#### Information and training for professionals:

The seniors's residents and catering professionals will all be informed of the project by the project leader during plenary meetings organized on each site (3 plenary meetings per site). After this information, FIFO referents will be identified in each seniors's residents (1IDE, 2 AS and 2 MM per seniors's residents) and will be trained by the project leader. They will act as an interface between the care team and the professionals of the clinical research unit and will constitute a project resource in each seniors's residents.

### STEP 1 : M-1 - M0

This step includes resident selection, resident unopposed, and evaluation before randomization.

• Inclusion of residents

Once the regulatory authorizations have been obtained (CPP, CNIL), the residents of the CHD Vendée's seniors's residents will be selected from all the residents meeting the inclusion and non-inclusion criteria. Then each resident and/or family/guardian will be informed by the principal investigator of each seniors's residents and a note of information and non-objection will be given to them (Appendix 2).

Initial assessment

The project will evaluate with the residents involved in the project:

**Nutritional indicators:** Nutritional intake (qualitative measurement of ingesta), weight, BMI, biological indicators, MNA screening score

Associated comorbidities: Number of wounds and pressure sores, number of falls

Autonomy: Autonomy of feeding and physical or psychological autonomy

Behavior around the meal

Resident satisfaction / enjoyment of food

Hospitality/care workload of seniors's residents professionals

Significant events on dietary intake, MAP, NOD, laxatives and any hospitalization will be tracked during this period.

#### STEP 2 : M0 – M6

• M0 : Implementation of « hand-held » or traditional feeding depending on the randomization arm of the resident.

This step consists in setting up the "finger-food" vs traditional food according to randomization, on the 3 sites of the CHD Vendée, after information/training of the ad-hoc professionals (care services, catering).

The same manufacturing process is planned for all 3 sites.

The distribution of this offer will be ensured by the catering of each site to the services concerned (in individual, nominative trays). The temperature of the food will be adapted to allow consumption with the hands.

At the beginning of this stage (M0), each resident included in the arm with "finger-food" will receive the 2 main meals (lunch and dinner) in the form of finger foods. Those included in the arm without "finger-food" will have the food offer as usually proposed. Breakfast remains the same as usual.

2 types of "finger-food" are planned in the study, depending on the feeding abilities of each resident (normal texture or modified texture) :

- The "classic hand-eater" for residents who are able to eat with a normal texture but have praxis problems and/or physical handicaps.

The proposed food offer will allow to grasp with the fingers, the dishes presented in the form of reduced portions. A diversity of presentation types is planned: food cut into cubes, slices, or sticks (raw vegetables, fruits), meatballs, fish croquettes, surimi, flans, quiches, quenelles, fritters, toasts, terrines, cheese, yoghurt drinks, compote drinks, ice cream sticks, cookies... The composition in macronutrients and in particular the caloric and protein contributions, will be identical and preserved between the "classic" menu and the "classic eat-in" menu.

- The "smooth mixed feed" for residents who are unable to eat with a normal texture because they are edentulous and/or have oral pathologies and/or swallowing problems.

In this case, it will be the variation of the "mixed" meal in "eat-in" presentation, in the form of bites, whose consistency has been modified with the use of vegetable gelatins. They will be presented in the form of small portions that can be consumed in 1 to 2 bites. The composition in macronutrients and in particular the caloric and protein contributions, will be identical and preserved between the menu "usual mixed smooth" and the menu "eat hands mixed smooth".

In order to maintain the sensory perception of the meals, the bites will be differentiated by their tastes, colors, smells and shapes. A standard presentation of the meal will be proposed (hot/cold and salty/sweet). A thick sauce will be added to the bites to avoid the meal being too dry.

The proposed offer will be identical for all residents, according to texture; the prevalent aversions of this population having been identified beforehand and removed from the food offer.

• Resident follow-up

The project will evaluate with the residents involved in the project:

**Nutritional indicators:** Nutritional intake (qualitative measurement of ingesta), weight, BMI, biological indicators, MNA screening score.

Associated comorbidities: Number of wounds and pressure sores, Number of falls

Autonomy: Autonomy of feeding and physical or psychological autonomy

Behavior around the meal

Resident satisfaction / enjoyment of food

Hospitality/care workload of seniors's residents professionals

Significant events on food intake, LDCs, laxatives and any hospitalization will be tracked during this period.

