In addition, this concept could reduce food waste, which is important in seniors's residents,

due to a service that is not always adapted to the expectations and needs of residents [19]. In this national context, according to the National Institute of Statistics and Economic Studies

(INSEE), "the Vendée could see the number of people aged 60 or more double between 2007 and 2040, to reach 310,000 inhabitants: seniors would then represent 36% of the Vendée population" [20]. Moreover, the number of people over 80 years old will increase by 57,000 between 2010 and 2040. The department of Vendée will thus experience, along with Loire-Atlantique, the most significant aging in the Pays de la Loire region [21].

An Evaluation of Professional Practices (EPP) relating to undernutrition carried out at the CHD Vendée highlights a significant prevalence of undernutrition or its risk, regardless of the medical and surgical sectors, and concerns 30 to 50% of patients (source: data communicated by the Dietetics and Nutrition Unit of the CHD Vendée).

As the proportion of elderly people is high in these sectors, the prevalence of undernutrition in seniors's residents can be estimated at one in three or even one in two patients. A survey conducted by the CHD Vendée catering service showed that 30% of long-stay patients have a modified texture diet. In addition, 20% of meals in the Long-Term Care Unit (USLD) are not consumed (source: data provided by the CHD Vendée catering service). To remedy this problem, the CHD catering service has received theoretical and practical training for a new presentation of modified textures. The tests carried out with the patients following this training were well perceived with 3 positive points noted: increase in the quantities eaten, increase in the time spent at the table, socialization of the patients. This multidisciplinary research project proposed at the CHD Vendée is part of a desire to consider food as a care in its own right and supports the institutional work of individualizing the care of the resident, via the personalized life project developed for each of them within these structures.

The main objective of this study is to evaluate the added value of "finger-food" on the nutritional intake of seniors's residents who are unable to eat with cutlery and/or who require stimulation of food intake and/or assistance with meal preparation.

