### 3.2 STUDY DIAGRAM

# 3.3 RANDOMIZATION

The randomization will be done via the Clinsight software by connecting to the website: https://nantes-lrsy.hugo-online.fr/CSOnline/.

The connection will be done thanks to a login, a password and a study number, delivered by a data-manager of the Research Promotion Department of the CHD of La Roche/Yon.

The following information must be filled in:

- First initial of the name
- First initial of the first name
- Date of birth
- Compliance with inclusion and non-inclusion criteria (yes/no)
- Collection of non-objection (yes/no).

The inclusion number will be assigned automatically during randomization. An e-mail confirmation will be sent to the person who performed the randomization and to all the persons concerned.

The randomization list will be carried out by a statistician from the Research Promotion Department of the CHD of La Roche/Yon.

A guide to the randomization procedure will be available online under Clinsight.

Randomization will be stratified by center (seniors's residents) and performed in a 1:1 ratio.

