# 4. STUDY POPULATION

# 4.1 DESCRIPTION OF THE POPULATION

All the residents of the CHD Vendée seniors's residents who meet the inclusion criteria will be able to be included in the "FIFO" trial:

- La Roche-sur-Yon : Le Marais, La Plaine
- Luçon : La Roseraie, L'Olivier
- Montaigu : Augereau, Le soleil de la Maine

Of the 269 residents institutionalized in these facilities, we estimate that about 60 subjects meet all the criteria.

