### Primary endpoint :

The evolution of caloric and protein intakes between inclusion and 6 months will be compared between the 2 groups by a Wilcoxon Mann-Whitney test.

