### 6.2.7 Choice of subjects to be included in analysis

All residents included in the study will be analyzed.

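### Texture need decides which finger-food product a resident gets, but it is not recorded at baseline or used in the primary analysis: a modest loss of precision and of information

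*Combined protocol and SAP*

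**What the plan says.** Section 5.1, Step 2, plans two products: "2 types of 'finger-food' are planned in the study, depending on the feeding abilities of each resident (normal texture or modified texture"). The smooth mixed type is for residents "unable to eat with a normal texture because they are edentulous and/or have oral pathologies and/or swallowing problems". Each type has its own comparator, the usual menu of the same texture, with the same calorie and protein content.

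Section 3.3 states: "Randomization will be stratified by center (seniors's residents) and performed in a 1:1 ratio". The items entered at randomisation are initials, date of birth, "Compliance with inclusion and non-inclusion criteria (yes/no") and non-objection. Texture is not among them. Nor does it appear in the initial assessment (section 5.1, Step 1) or the study schedule (section 5.2). The photo analysis in section 2.1.3 classifies dishes by course, not by texture.

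Under section 6.2.1, the changes in calorie and protein intake "will be compared between the 2 groups by a Wilcoxon Mann-Whitney test". No covariate, stratum or subgroup is named there or for the secondary endpoints. Section 6.2.7 adds: "All residents included in the study will be analyzed".

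On numbers, section 4.1 says: "Of the 269 residents institutionalized in these facilities, we estimate that about 60 subjects meet all the criteria". The only figure on how common modified texture is comes from a catering survey reported in section 1.1: "30% of long-stay patients have a modified texture diet".

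**The concern.** Texture need is fixed before allocation, determines which product and which comparator menu a resident receives, and marks oral and swallowing problems that could affect the six-month course of intake. Section 1.1 makes different effects by patient type plausible: it reports an earlier hospital evaluation in which finger-food seemed to help only some patients.

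Three things are at stake. If texture predicts the change in intake, an analysis that ignores it is less precise than it could be. In a trial of about 60, the arms may differ noticeably in texture mix, and the estimate from that particular trial then shifts. Finally, the pilot is meant to supply preliminary data and hypotheses for later work, and the planned results would give no indication of which product to take forward.

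**Working it through.** The plan gives no sample-size calculation (section 6.2.2), so there is no figure to reproduce.

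**Inputs from the documents:** about 60 residents, 1:1, so 30 per arm; 5% significance level; 30% modified texture as a starting value.

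**Assumptions:** two-sided test; 20 to 50% modified texture among eligible residents, because the 30% describes long-stay patients; a gap between texture groups in intake change of 0.3 to 0.8 SD; a treatment effect of 0.75 SD for power. SD means the within-texture SD of the change.

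**1. Chance imbalance in texture share.** SD of the arm difference = sqrt(2 × 0.3 × 0.7 / 30) = 0.118, or 11.8 points. An imbalance of 20 points is 6 residents in 30.
- If each arm's count is an independent binomial at 30%, P(≥20 points) = 12.0%.
- If exactly 18 of 60 have modified texture (hypergeometric), it is 15.8%.
- With 12, 24 or 30 of 60, it is 10.4%, 18.7% or 19.6%.
- Simulated stratification by home (6 homes of 10) leaves the 15.8% unchanged.

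**2. Shift in a trial with that imbalance.** Shift = imbalance × gap = 0.20 × 0.3 = 0.06 SD, up to 0.20 × 0.8 = 0.16 SD. The standard error of the arm difference is sqrt(2/30) = 0.26 SD, so the shift is 0.06/0.26 = 0.2 to 0.16/0.26 = 0.6 of a standard error.

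**3. Type I error of the planned test.** By simulation it is 4.3 to 4.9% overall, for gaps of 0, 0.5 and 1.0 SD. Among trials with an imbalance of 20 points or more, it is about 6% at a gap of 0.5 SD and 10% at 1.0 SD.

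**4. Precision.** The share of outcome variance due to texture is 0.21d²/(1 + 0.21d²), where d is the gap and 0.21 = 0.3 × 0.7. It is 1.9% at d = 0.3 and 11.8% at d = 0.8. Simulated power, with 18 of 60 on modified texture and a 0.75 SD effect:

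| Gap (SD) | Planned Wilcoxon | Texture-stratified (van Elteren) |
|---|---|---|
| 0 | 79% | 78% |
| 0.3 | 78.5% | 78% |
| 0.5 | 77% | 78% |
| 0.8 | 73.5% | 78% |
| 1.0 | 71% | 78% |

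Over the 0.3 to 0.8 range the planned test loses about 0 to 6 points against no gap. Stratifying the test costs about 1 point when texture does not matter and recovers about 4 points at 0.8 SD.

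**5. Different effects by texture.** If only normal-texture residents gain 0.5 SD, the pooled effect is 0.7 × 0.5 = 0.35 SD. If only they gain 0.75 SD (gap 0.5 SD), power falls from about 77% to 47%, and the texture-stratified test also has 47%.

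**6. What results by texture can show.** With 42 normal-texture and 18 modified-texture residents, the 95% half-widths are t(40) × sqrt(2/21) = 0.62 SD and t(16) × sqrt(2/9) = 1.00 SD. The difference between texture-specific effects detectable with 80% power is 2.80 × sqrt(2/21 + 2/9) = 1.58 SD.

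**The case against.** A reader might infer that the primary comparison is biased or invalid. The documents do not support that: allocation is random and 1:1, and the unadjusted test holds its 5% level on average. The shift in step 2 applies to an unlucky realised trial and is smaller than the sampling error. The endpoint is a change from inclusion, so stable differences in intake level between texture groups largely cancel, and only a different trajectory counts. This stands.

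A reader might also infer that mixing two products makes the result uninterpretable. It does not. The objective concerns finger-food as an offer, and each product is set against a usual menu of the same texture and composition. The pooled contrast is therefore the average effect of a texture-adapted service. Nor would adding texture as a main effect undo a mixed effect, as step 5 shows. Results by texture will be too imprecise to settle which product works.

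A third tempting step is to fault the randomisation. Six homes by two textures gives 12 strata for about 60 residents, about 5 each, so stratifying by home alone is defensible.

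What survives is narrower. The plan neither records nor uses a pre-allocation characteristic that decides the product received, although using it is cheap and texture-specific estimates would serve a pilot's purpose.

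**Conclusion.** The point holds as a minor improvement to the analysis. Texture is absent from the listed baseline data and from the primary test. The consequences are a power loss of about 0 to 6 points, a conditional shift of about 0.06 to 0.16 SD in the roughly 10 to 20% of trials with a 20-point imbalance, and no information on which product worked. These sizes rest on the assumed 0.3 to 0.8 SD gap, the 0.75 SD effect and a 20 to 50% share of modified texture. None of the three is given for eligible residents. If texture does not predict the change in intake, only the missing information remains.

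**What to change.** - Record texture need in the CRF before randomisation. Section 5.2 places randomisation between M-1 and M0 and the trial is open, so a value taken at M0 could follow allocation. Tabulate it by arm.
- Prespecify texture in the primary comparison. If a rank test is kept, use a texture-stratified (van Elteren) Wilcoxon test. If a model adjusted for baseline intake and residence replaces the Wilcoxon test, add texture as a covariate. The current plan contains no such model, so the second route changes the primary method rather than adding a term to it.
- Report the kcal and protein differences between arms with 95% CI by texture, labelled descriptive, without subgroup tests.
- Leave randomisation as it is.

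The cost is one CRF field, which catering must already know to prepare individual named trays, and one degree of freedom in a model (or about 1 power point for the stratified rank test if texture is not prognostic). The subgroup intervals will be wide, about ±0.6 SD for normal and ±1.0 SD for modified texture at a 30% share, and the report should say so.

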### 5.2 STUDY SCHEDULE

Actions		Inclusion	M-1 to M0	M0 to M1	M1 to M2	M2 to M3	M3 to M4	M4 to M5	M5 to M6
Collection of non-opposition Size measurement		X							
Randomization			х						
Collection of consumption: nutritional intake*.			х	х	х	x	х	х	x
Nutritional Indicators**			x	x	Х	Х	х	x	х
Nutritional Indicators***			Х						х
Associated comorbidities ****			Х	Х	Х	Х	Х	Х	Х
Autonomy	Power supply (EBS)		Х			Х			Х
Autonomy	GIR		Х						Х
Eating behavior (Blandford scale)			Х			x			х
Resident satisfaction (VAS of faces)			Х	Х	Х	X	Х	Х	x
Impact on professionnals			Х	Х	Х	X	Х	Х	x
Significant events on food intake *****			Х	Х	Х	Х	Х	Х	Х

\*3 consecutive days, for lunch and dinner, at a time t between M-1 and M0, then monthly

\*\*Weight, BMI \*\*\* Biological indicators (albumin/ pre-albumine/ CRP), MNA screening score \*\*\*\* Number of pressure score and severity, number of falls, infectious complications: over the entire study period \*\*\*\*\* Medical and environmental events, drug consumption, hospitalization (number, reasons, duration)

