A prospective survey carried out in 67 French seniors's residents on the nutritional status of 1550 residents highlighted the need for assistance with meals for 31% of the subjects [3]. Many of them progressively lose their appetite, with the onset or even worsening of undernutrition, a real public health problem in seniors's residents. A 2011 French study [4], involving 57 seniors's residents and 4520 residents with an average age of 85.8 ± 7.8 years, showed that 45.6% (44.2% - 47.1%) of the residents had undernutrition, including 12.5% with severe undernutrition. In addition, dependence on food was the characteristic that most discriminated between undernourished residents and others (+23.9%). According to P. BROCKER3 , the prevalence of undernutrition in institutions varies between 15 and 38% [5]. M. FERRY4 estimates that the prevalence of undernutrition can reach 70% of elderly patients in hospitals [6].

According to the Agence Nationale d'Accréditation et d'Evaluation en Santé (ANAES), protein-energy undernutrition results from an imbalance between the body's protein-energy intakes and needs [7]. The Haute Autorité de Santé (HAS) [8] defines the diagnosis of undernutrition according to the existence of one or more of the following criteria: weight loss  $\geq 5\%$  in 1 month and/or  $\geq 10\%$  in 6 months and/or Body Mass Index5 (BMI) < 21 and/or Albuminemia < 35g/I (to be interpreted taking into account the C-reactive Protein (CRP)) and/or overall Mini Nutritional Assessment6 (MNA) < 17. Undernutrition is characterized as severe if weight loss  $\geq 10\%$  in 1 month and/or  $\geq 15\%$  in 6 months and/or BMI < 18 and/or Albumin < 30g/I.

Undernutrition leads residents into a vicious circle, as described by M. FERRY [9]; a vicious circle that is self-perpetuating between the causes and consequences of undernutrition. The risks of comorbidities and mortality increase [10], with an increased risk of bedsores and falls.

A study carried out on 8428 hospitalized patients, on the relationship between mortality and

BMI, shows a mortality three times higher in subjects aged 70 to 79 years, when the BMI was lower than 18, compared to a BMI between 32 and 40 [11].

In addition, the quality of life of the residents is altered [12] and they become more prone to develop swallowing disorders, food dependency, hunger sensation disorders and modified texture sometimes becomes necessary.

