#### Figure 1 – Satisfaction scale

Hospitality/care charge for seniors's residents professionals: at M-1 (on 3 consecutive days) then monthly on 3 consecutive days until M6, by the housekeeper according to:

- Average meal duration
- Hospitality load: Number of interventions by the professional per resident. The average number of interventions over the 3 days will be taken into account.

**Significant events on food intake** (medical, such as an acute episode; environmental, such as a death in the family,...), which may constitute a bias for the analysis of the results, will be traced throughout the study.

Also, a follow-up of the advance medical prescriptions (AMP), oral nutritional supplements, laxatives will be carried out during the whole study.

In addition, any hospitalization, its duration and reason will be traced during the study.

This information, traced by the professionals of the service (patient file / Medical Object) will be recovered by the clinical research IDE.

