# 5.3 RULES FOR DISCONTINUING SUBJECT PARTICIPATION

### 5.3.1 Criteria for premature termination of an individual's participation in study

All residents included in the protocol who no longer wish to participate will be removed from the study as soon as this request is made.

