### 6.2.5 Consideration method for missing, unused or invalid data

The main criterion being the comparison of the evolution of the quantity of ingesta between the inclusion and the 6 months of follow-up, a missing value of these data will entail an imputation of this one by the worst value then, by the average of its group.

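### A resident's death is not a named data item, and section 6.2.5 fills the missing month-6 intake of a resident who has died with the average of the arm's observed residents, which is unsound for deaths

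*Combined protocol and SAP*

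**What the plan says.** The combined protocol and SAP names one route out of the study. Section 5.3.1 covers residents "who no longer wish to participate will be removed from the study as soon as this request is made". Neither death nor transfer is listed.

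The footnotes to the schedule in 5.2 give the items recorded over time: "Medical and environmental events, drug consumption, hospitalization (number, reasons, duration", and pressure sores with "number of falls, infectious complications: over the entire study period". Section 2.2.2 adds events that may affect food intake. The only death it mentions is a relative's: "environmental, such as a death in the family". Mortality otherwise appears only in the rationale (1.1), which says of undernutrition: "The risks of comorbidities and mortality increase".

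Two rules then apply to everyone. Section 6.2.7 states "All residents included in the study will be analyzed". Section 6.2.5 states that for the main criterion "a missing value of these data will entail an imputation of this one by the worst value then, by the average of its group". Section 6.2.1 compares the change from inclusion to 6 months by a Wilcoxon Mann-Whitney test, and section 6.2.3 sets the level at 5%. Section 6.2.5 addresses only the main criterion, so the secondary endpoints have no missing-data rule.

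**The concern.** A resident who dies before month 6 has no month-6 intake. Read together, 6.2.5 and 6.2.7 still require a value and do not separate this resident from one whose meal photographs were lost. In the average version the value is the mean of the residents in that arm who still have data.

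This has two consequences. The filled residents count as independent observations although they only repeat their arm's own mean, so the test treats the data as more precise than they are. And if residents whose intake is falling are more likely to die, the remaining mean rises, and the arm with more deaths gains most from the fill. The secondary endpoints, with no rule, default to whoever is still observed.

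Without a planned record of the date and reason of exit, the report may be unable to show whether either happened. The pilot would also not reliably supply deaths and exits by arm for planning the later study.

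**Working it through.** **No planned figure to reproduce.** Section 6.2.2 says that no calculation was made. The figure of about 60 residents (4.1) is an estimate of how many are eligible.

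**Inputs from the plan.** About 60 residents; 1:1 allocation (3.3), so 30 per arm; Wilcoxon test (6.2.1); 5% level (6.2.3), taken as two-sided; all residents analysed (6.2.7); fills as in 6.2.5.

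**Assumed inputs.** Change in intake ~ N(-50, 200²) kcal in both arms, so no true effect. Those who die are the frailest, and frailty has correlation r with decline in intake. Worst value is read as the worst observed overall. The documents give no death rate, SD or correlation.

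**How many deaths.** With annual mortality a, expected deaths over 7 months are 60 × (1 − (1 − a)^(7/12)), which gives 7.3, 11.3 and 15.5 for a = 20%, 30% and 40%. The initial assessment precedes randomization (5.1, step 1), so only about 6 months can differ by arm. With exponent 6/12 the figures are 6.3, 9.8 and 13.5. The scenarios with 8 or 9 deaths lie within this range.

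**Deaths falling at random (8 of 60).** Average fill gives a two-sided type I error of about 11%, with a mean shift of about 1 kcal or less. Lowest rank or survivors-only gives about 4–5%. A rough check for a test of means: with k = 4 of n = 30 filled per arm, the apparent standard error is about (n − k)/n = 26/30 = 0.867 of the true one. The cut-off 1.96 then acts like 1.96 × 0.867 = 1.70, a two-sided error of about 9%. The Wilcoxon result is of the same order.

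**Unequal deaths, average fill.** Finger-food is the arm with more deaths. A favourable result is one that is significant for finger-food (nominal 2.5%).

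| Deaths | r | Mean shift | Favourable |
|---|---|---|---|
| 6 v 2 | 0 | −0.6 kcal | 5.1% |
| 6 v 2 | 0.5 | +21 kcal | 11.8% |
| 6 v 2 | 0.8 | +33 kcal | 17.6% |
| 6 v 3 | 0.5 | +14 kcal | 10.2% |
| 3 v 3 | 0.5 | about 0 | 4.6% |

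The r = 0 row separates the two effects. About 5% arises from the shrunken variance alone. The rise from about 5% to about 12% is due to selective death.

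**Same scenarios, other handling.**
- Lowest rank gives at most 0.4% favourable results in the 6 v 2 and 6 v 3 cases. Worst-value fill agrees with it to within about 0.1 percentage point.
- Lowest rank has its own cost. With 6 v 2 deaths unrelated to intake, about 9% of results are significant against the arm with more deaths; at r = 0.5 it is about 5%.
- Survivors-only keeps the same mean shift as average fill, because filling with the mean does not move it. Favourable results are about 5–9% in the unequal, correlated cases.

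**A different death model agrees.** Let the log-odds of death rise by 0, 1 or 2 per SD of decline, with 20% against 10% deaths. Average fill then shifts the difference by 0.00, +0.07 and +0.12 SD, with 6%, 11% and 13% favourable results. With 10% deaths in both arms the two-sided error is still about 8–10%. Worst-value fill at 20% against 10% moves the difference the other way, by −0.22 to −0.09 SD.

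**The case against.** The strongest reply is that 6.2.5 names the worst value first. In a Wilcoxon test that fill is almost the same as ranking deaths lowest, so much of the remedy is already in the plan and the harm arises only where the average fill is used. This stands, and it limits the point to the average fill. It does not remove the point: the plan does not define worst, does not say which fill decides, and as written applies the average to deaths too.

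A reader might infer that the plan tilts the trial towards finger-food. The documents do not support that. The shift needs an unequal split of deaths and a link between death and falling intake, and no passage suggests that finger-food raises mortality. If 8 deaths fall at random, the chance that 6 or more land in a given arm is about 13%, and over all splits neither arm gains. Nor should the whole gap between 2.5% and 12% be put down to selective death.

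A reader might also infer that deaths will go unrecorded. The documents do not show this either. Medical events and hospital stays are traced from the resident's file by the research nurse (2.2.2), and section 6.1.1 requires the CRF to hold the data needed for analysis. The CRF is not among the documents. What can be said is that the protocol specifies no field, date, reason or comparison by arm.

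Finally, this is a pilot and mortality is not an objective. That bears on the weight of the point, but deaths and exits by arm are basic information for a pilot to provide.

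**Conclusion.** The point holds in a limited form. The protocol does not name the resident's death, or the date and reason of exit, as collected items, and 6.2.5 handles death like any other gap. The average fill is wrong for deaths whatever their cause: under the assumed inputs it gives about 11% two-sided error at a nominal 5%, with no imbalance needed. A tilt towards the arm with more deaths (about 21 kcal and 12% favourable results at 6 v 2 and r = 0.5) is conditional on an unequal split and on deaths linked to declining intake. The worst-value fill, read as the worst observed overall, does not have the fault.

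The gaps in the text are certain. The sizes rest on assumed mortality, SD and correlation, and show order of magnitude only. The change should be made, because it is cheap and the average rule gives a wrong error rate.

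**What to change.** 1. In 5.2 and 5.3, add an end-of-participation item: date and reason (death, transfer out of the six homes, objection by resident or family, other). Report deaths and exits by arm.
2. In 6.2.5, state that an intake missing because of death is never filled with the group average. Keep the plan's worst-value step for deaths, defined as the lowest rank in the existing Wilcoxon test.
3. Beside it, show a survivors-only result as a stated sensitivity analysis, with deaths by arm. Show deaths by arm beside each secondary endpoint as well.

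The cost is one CRF page, filled from a file the research nurse already consults, and a few sentences in 6.2.5. Care, randomization and the test are unchanged. The downside should be stated in the plan. Lowest rank mixes survival with intake and can count against the arm with more deaths (about 9% significant unfavourable results at 6 v 2 deaths unrelated to intake). Survivors-only carries the same mean shift as average fill when death depends on intake. Neither is sufficient alone, so the two must be read together.
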